## 1.3 SCHEDULE OF ACTIVITIES (SOA)

## TIMELINE OF STUDY ASSESSMENTS AND PROCEDURES:

Assessment/Procedure	Online/Phone Screen	Remote/In Person Screen (at Duke) - can be split in 1-2 visits (part remote/part in-person)**	Pre-Tx fMRI (at UNC)	Intervention therapy sessions at Duke) 	Wks 4, 8 & 12 (if applicable) 	fMRI (wk 8 & 12) 	Study Completion Visit-Part I (Duke)	Part II Post-Tx fMRI (UNC)
Online/Phone Screen Questionnaire	X							
Informed consent		X (via Duke REDCap econsent)	X (UNC specific consent)					
SHAPS	X	X	X	X	X	X	X	X
C-SSRS		X			X (post)		X (post)	
SCID5 relevant to inclusion /exclusion, NART		X						
SCID-5-RV		X						
[name] & Background info, CGI-S, CTQ		X						
R61 Phase: BDI-II, BAI, SF-36, PhenX depression & perceived stress, PCL-5, PSWQ, IDAS, TMS, SRS-2		X			X		X	
R33 Phase: BDI-II, BAI, SF-36, PhenX depression & perceived stress, PCL-5, PSWQ, TMS, MAPS, IDS-RS, BADS		X			X		X	
R33 Phase: WAI					X		X	
EEfRT, PRT		X			X		X	
Caffeine, Nicotine, Alcohol & sleep day of intake		X	X		X	X	X	X
Urine Pregnancy Test; PEERS (female only)			X (pre)			X (pre)		X (pre)
CGI-I, % homework tasks completed				X			X	
MID			X 			X		X
fMRI			X 			X		X
MRI checklist			X			X		X
Urine Drug Screen		X**						
Acceptability Questionnaire							X	

Between 8-15 weeks of therapy sessions (therapy will be either MBCT or BATA), in-person or remote during COVID-19 guidelines.

At visits week 4, 8 & 12 (if applicable), subjects will complete EEfRT & PRT computer tasks at the beginning of the visit followed by the therapy session or if during COVID-19 times, at a separate in-person visit from the remote therapy session. All paperwork done at therapy visits will be done in addition to procedures noted in this column. They will then complete the REDCap questionnaires at these key assessment time points (either in-person or done remotely by REDCap survey invitation). If the final therapy visit is before week 8, there will be three assessment points (pre-treatment, week 4, and at the last therapy visit). If the final therapy visit is between week 8 and week 12, there will be four assessment points (pre-treatment, week 4, week 8, and at the last therapy visit). If the final therapy visit is after week 12, there will be five assessment points, and post-treatment assessments will be administered either at the last therapy session or separately if therapy was remote. COVID-19

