**Aims 3, 4, and 5 pertain to all 210 participants randomized (n=105 to receive BATA and n=105 to receive MBCT).**

Aim 3: We predict that BATA will produce clinically and statistically significant improvements in anhedonia and functional outcomes that exceed those due to the comparison treatment.

Aim 4: We predict that BATA will improve behavioral indices of reward sensitivity.

Aim 5: To evaluate the effects of BATA versus a comparison treatment on neural response to rewards. We predict that, consistent with Aim 1, BATA will increase right CN activation during reward anticipation and decrease rACC activation during reward outcomes and that BATA will not decrease amygdala activation to threat, confirming the specificity of BATA for targeting these positive valence neural systems. This Aim will provide a replication and extension of Aim 1 findings with a larger sample and with an optimal treatment dose.

In the PET sub-study, Hypothesis 1- BATA, but not the comparison treatment, will result in increased phasic striatal DA release but will not influence background DA striatal tone. Hypothesis 2- that normalization of fMRI-derived mesocorticolimbic activation due to BATA specifically will be associated with increased phasic DA release but no change in background DA tone during incentive processing.

This is not a pilot study but rather a Phase I/II study. The R61 phase (Phase I) of the protocol is designed to provide preliminary data for the acceptability, identification of the optimal dose of BATA as well as the preliminary efficacy of BATA in subjects with anhedonia compared to those in the MBCT control group. Using the fMRI data, this phase of the study will test if BATA produces changes in neural responses to reward anticipation and reward outcomes that exceed changes in the MBCT group and does not impact neural responses to threat. As such, a small group (N = 60) of subjects will be in this blinded phase and they will complete up to a total of 4 fMRI scans (pre-treatment, week 8, 12 and post-treatment). The R61 study will be entering a no-cost extension at the end of the current project period to allow for completion of data collection for this phase. Due to limited funds, the number of scans obtained is being reduced from up to 4 scans to two scans (pre- and post-treatment.) for participants

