##### **Eligibility and diagnostic assessment measures:**

**1) The Columbia Suicide Severity Rating Scale (C-SSRS)** will be administered. Participants indicating "yes" on items 4 (Active Suicidal Ideation with Some Intent to Act, without Specific Plan) and/or 5 (Active Suicidal Ideation with Specific Plan and Intent) within the last month will be excused from the trial and referred to more intensive clinical management. The C-SSRS will be used during the initial assessment visit over the past 1 month and then used to assess "since the last study visit" at the in-person assessment visit, if applicable during COVID-19, and the weeks 4, 8, 12 therapy visits that include the computer tasks and the final therapy/post-treatment visit. During the 1-2 remote & in-person assessment screening visits, if the participant has a 4 or 5 on the CSSRS, they will no longer be eligible for the study as per inclusion/exclusion criteria. **COVID-19 Update:\*\*Please note that the conduct of the CSSRS with computer tasks at the inperson assessment visit, wks 4, 8, 12 and final visit and are contingent upon the building availability and approval of in-person visits either at Duke or UNC. If not available and approved, the computer tasks with CSSRS will be omitted until the study team have the appropriate approvals to do the tasks at an in-person visit. These omissions (skipping the inperson visit) will not be considered protocol deviations since the omissions are necessary to be able to open the study and begin to collect the main primary outcomes of imaging and therapy.**

**2)** The SHAPS will be repeated to verify a score of  $\geq 30$ , corresponding to clinically significant anhedonia. **If the SHAPS score is  $<30$ , the participant will be ineligible (R33 phase);**

**3)** Clinician's Global Impression Scale-Severity score (CGI-S) = 3 to assure a clinically impaired sample. If the CGI score is 2 or less, the participant will be ineligible;

**4)** The Structured Clinical Interview for DSM Disorders-5 Research Version (SCID-5-RV) will be administered to assess exclusionary conditions and to characterize the sample. Individuals with primary anhedonia but no DSM diagnosis will be included. Exclusionary axis I disorders include:

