### 5.3 SCREEN FAILURES

Screen failures are defined as participants who consent to participate in the clinical trial but are not subsequently randomly assigned to the study intervention or entered in the study.

Screen failures who did not meet inclusion/exclusion criteria at the first visit will be allowed to return to Duke to rescreen for the study up to a total of 3 times, if it is deemed appropriate (examples include SHAPS<30, UA drug screen is positive at screening but the subject doesn't meet criteria for abuse or dependence, CGI-S <3, C-SSRS items #4 or 5 as yes, current psychotropic medication use, positive urine pregnancy screen with delivery of child and female subject is eligible again, etc).

Any participant going over 4 weeks between the remote assessment and the 7T pre-treatment scan, will be considered a screen fail and not randomized and have the ability to rescreen at a later date (i.e. will sign another econsent, redo SHAPS, C-SSRS, UA drug screen [if possible during COVID times], all self-report, SCID5, THI and computer tasks [if possible & contingent on ability to have in-person visits]). Their NART will not be redone and can be used for the rescreen.

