### 6.3 MEASURES TO MINIMIZE BIAS: RANDOMIZATION AND BLINDING

Randomization assignment will be performed through a dynamic balancing protocol that will balance treatment assignment within groups of lower (20-30) and higher (31+) SHAPS scorers. We recognize that anhedonia is common in patients with major depression. To ensure a true transdiagnostic sample, we will monitor DSM diagnoses of enrolled subjects in both phases to ensure that no more than 40% in either phase meet DSM criteria for a current depressive episode. We will stratify groups based on SHAPS scores. **For the R33 phase**, we will no longer stratify groups based on SHAPS score as all participants will have SHAPS scores 30 or greater.

Unblinding does not apply to this study since study therapists and participants are aware of which group the participant is in for the therapy intervention.

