**Aim 2:** We will analyze whether dose moderates treatment response via regression models that predict change in neural target (CN and dACC) activation from the number of sessions as an indicator of BATA dose. Hierarchical linear modeling where time-in-weeks is treated as a continuous variable nested within subject will provide parameter estimates of the linear, quadratic, and cubic functions for change over time in neural target engagement over the course of treatment. Standard evaluation (e.g., significant at  $p < .05$ ) will guide our selection of the most appropriate function. From these functions, we can estimate both the point in time where the change in target engagement is greatest and where it approaches 0, meaning minimal further improvement is anticipated. Although mid-treatment scans will occur at weeks 8 and 12, we will estimate change continuously so the optimal dosage is not restricted to one of those timepoints.

**Aims 3 and 4:** To evaluate the efficacy of BATA, relative to MBCT, for treating anhedonia, functional outcomes, and behavioral indices of reward sensitivity, we will test for differential change over time between those who receive BATA and those who receive MBCT post-treatment. We will use an intent-to-treat (ITT) analysis for patients who receive BATA relative to those who don't. The ITT model will be a repeated-measures ANCOVA with effects for treatment condition (BATA, MBCT), outcome measure (SHAPS, PRT, etc), time (pre-treatment, post- treatment) and their interactions. The interaction tests will assess mean differences at each time point as well as differences in the degree of change between the groups. This also provides tests of each group relative to their baseline scores. We will include gender and age as covariates in these models. \*\*We will also note any participants who were enrolled in the study and had PRT & EffRT reward tasks data omitted during COVID-19 times.

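### SHAPS is both the R33 entry cut-off and an outcome, so the planned tests of each arm against its own baseline can show improvement from regression to the mean alone

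*Combined protocol and SAP*

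**What the plan says.** **Selection on SHAPS.** Section 4.2 says "The SHAPS will be repeated to verify a score of" at least 30, with lower scores ineligible in R33. Section 5.1 lists the same threshold. Section 6.3 says that in R33 "we will no longer stratify groups based on SHAPS score as all participants will have SHAPS scores 30 or greater". Under section 5.3, screen failures, with SHAPS below 30 as a named example, "will be allowed to return to Duke to rescreen for the study up to a total of 3 times" where that is judged appropriate.

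**SHAPS as outcome.** The synopsis lists pre/post change in SHAPS among the primary endpoints. For Aims 3 and 4, section 9.2 specifies a repeated-measures ANCOVA whose stated purpose is comparative: "we will test for differential change over time between those who receive BATA and those who receive MBCT post-treatment". It then adds: "This also provides tests of each group relative to their baseline scores".

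**Baseline.** The Schedule of Activities (section 1.3) marks SHAPS at the online/phone screen, the assessment visit and the pre-treatment scan visit. Section 9.2 says only pre-treatment and does not choose among them. The documents do not mention regression to the mean.

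**The concern.** A score that had to clear a threshold is, on average, too high for the people who cleared it. Measured again, it tends to fall even if nothing has changed. Testing each arm's post-treatment SHAPS against a baseline that served as the entry criterion therefore has a null expectation above zero, and nothing in the design shows how much of the fall is of this kind. The comparator is an active therapy. If the arms did not differ but both fell significantly, a report could present that as both therapies working, which these within-arm tests cannot establish.

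**Working it through.** **1. The plan's own power figure.** Section 9.1 gives 65 per arm (N = 130), two time points, correlation ρ = 0.35 and α = .05. For the group-by-time interaction, λ = f²·N·m/(1 − ρ) with m = 2 and df (1, 128).
- f = .20: λ = 0.04 × 130 × 2 / 0.65 = 16, power 97.8% (plan: 98%).
- f = .14: λ = 0.0196 × 130 × 2 / 0.65 = 7.84, power 79.4% (plan: 80%).

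Both reproduce, so the plan's power calculation is for the between-arm interaction. The same ρ and n are used below.

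**2. Regression to the mean with zero true change.** Assume bivariate normal scores in those screened, with equal variances, and a cut-off c SD from their mean. The qualifying score is the baseline.
- Mean of those who pass: m(c) = φ(c)/(1 − Φ(c)).
- Expected spurious fall: (1 − ρ)·m(c).
- Variance of change: (1 − ρ)²·Var(X | X > c) + (1 − ρ²), where Var(X | X > c) = 1 + c·m − m².

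Example, c = 0 and ρ = 0.35: m = 0.798; fall = 0.65 × 0.798 = 0.52 SD; variance of change = 0.4225 × 0.363 + 0.8775 = 1.031; standardised change = 0.519/1.015 = 0.51.

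The rates below are for a paired t-test at two-sided .05 with n = 65, counting only significant improvement (nominal 2.5% per arm). The arms are independent, so the rate for both is the square of the rate for one.

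| Cut-off relative to screened mean (share passing) | Fall, ρ = .35 | One arm | Both arms | Fall, ρ = .70 | One arm | Both arms |
|---|---|---|---|---|---|---|
| at the mean (50%) | 0.52 SD | 98% | 96% | 0.24 SD | 73% | 54% |
| 0.5 SD below (69%) | 0.33 SD | 71% | 51% | 0.15 SD | 37% | 14% |
| 1 SD below (84%) | 0.19 SD | 28% | 8% | 0.09 SD | 15% | 2% |
| 2 SD below (98%) | 0.04 SD | 4% | 0.2% | 0.02 SD | 4% | 0.1% |

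The cut-off positions and ρ = .70 are assumptions. The documents give neither the SHAPS distribution in those screened nor an untreated test–retest value.

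**3. Variants by simulation (4,000 trials per setting), cut-off at the mean.**
- Up to three attempts in total, every failure returning: fall 0.59 SD, both arms over 99% (ρ = .35); 0.32 SD, 86% (ρ = .70). Section 5.3 lets only some failures return, so this is an upper bound.
- Cut-off passed at both screen and verification: 0.42 SD, 83% (ρ = .35); 0.16 SD, 18% (ρ = .70).
- Baseline taken later and not used for eligibility, errors independent: mean fall about zero; one-arm rate 2.2–2.8% over all settings run.

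**4. The randomised comparison of change.** With no true effect it rejects in 4.5–5.4% of trials in every scenario, because the expected regression is the same in both arms.

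**The case against.** The strongest answer is that the plan's inference is already comparative. Section 9.2 states its purpose as differential change, and the within-arm tests are something the model also provides. Aim 3 in section 4.1 begins "We predict that BATA will produce clinically and statistically significant improvements in anhedonia and functional outcomes", which alone might suggest that within-arm significance would count as success. The sentence goes on to require that the improvements exceed those under the comparison treatment. A reader might infer that the efficacy conclusion rests on within-arm tests, or that the Aim 3 comparison is biased. The documents support neither reading. This part of the objection stands and limits the point to the unqualified within-arm SHAPS tests.

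The size is also open to challenge. Candidates are seeking treatment for anhedonia and complete an earlier screening SHAPS, so the cut-off may lie well below the mean of those assessed. The 0.35 comes from preliminary studies and may understate untreated stability; at ρ = .50 with the cut-off at the mean, the fall is 0.40 SD and the one-arm rate 93%. The R61 strata, "balance treatment assignment within groups of lower (20-30) and higher (31+) SHAPS scorers", imply weaker selection for some of the first 60. Section 5.1 states the threshold without limiting it to a phase, and the two passages should be reconciled. All this bears on how large the effect is, not on whether the plan guards against it.

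Finally, having no untreated arm is a design choice, not an error. That is correct, but it is also why within-arm change cannot be read as a treatment effect here.

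**Conclusion.** The point holds for within-arm inference on SHAPS. If the qualifying score is the baseline, a significant improvement with no true change ranges from near-certain to close to nominal, depending on a cut-off position that the documents do not give. It rests on approximate normality, zero true change and the stated correlations.

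Three stronger readings should not be drawn:
- That every participant is retested up to three times. Rescreening applies only to screen failures judged suitable to return.
- That a stated fraction of the pilot pre–post effect (d = 1.24) is regression. The standardiser of that d is not given, so it cannot be set against falls in screened-population SD units.
- That all outcomes are affected alike. PRT and EEfRT are not entry criteria and are touched only through any correlation with SHAPS.

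The change is worth making because it qualifies a test the plan states, at almost no cost.

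**What to change.** In section 9.2, Aims 3 and 4:

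1. State that efficacy conclusions rest only on the BATA–MBCT difference in change.
2. Report within-arm SHAPS change descriptively (mean and SD) with a regression-to-the-mean caveat, not as a significance test of improvement. The sentence on within-arm tests need not be removed for outcomes that did not select participants.
3. Name the analysis baseline: the SHAPS at the pre-treatment scan visit, where it exists. That visit follows eligibility and precedes randomisation (sections 4.1 and 4.2).
4. Imaging enrolment ended with the June 2022 amendment. For therapy-only participants without that reading, use the qualifying SHAPS with the caveat. For any future participant, take a SHAPS after eligibility and before allocation. A reading taken merely before the first session could follow open allocation and would put an unblinded baseline into the between-arm contrast.

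The cost is a few sentences, the loss of a within-arm p-value, and a baseline source that differs between imaging and therapy-only participants, under the same rule in both arms. A non-selecting baseline removes regression to the mean only. Natural recovery and expectancy remain in any within-arm change, so items 1 and 2 are needed even where item 3 can be met.

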### **Study Visits:**

Potential participants will complete the following:

- 1) A phone or online screen to determine initial eligibility via UNC's REDCap

- 2) A 1-2 clinical characterization visit(s) to determine eligible, and, if eligible, to characterize participants clinically. During COVID, can be split remote/in-person.
- 3) A pre-treatment 7 Tesla (7T) fMRI scan & if one of the first 60 subjects enrolled, have an initial blood draw of 10ml (2tsp). Update, the NARSAD blood protocol had entered an extension and has additional funds so up to 210 participants, in both phases, will have an initial blood draw of 10ml (2tsp). **As of 6/26/20, the blood protocol will no longer continue for any new participant enrolled in the study. As of the NCE 2022, this current amendment, imaging of new participants will end. Only enrollment into the therapy portion at Duke will continue.**
- 4) Patients will then be assigned randomly to the experimental treatment (BATA) or comparison treatment (Mindfulness Based Cognitive Therapy (MBCT)) for approximately 15 weeks of treatment.
- 5) The first 60 patients enrolled (n=30 who receive BATA and n=30 who receive MBCT) will additionally complete two additional, mid-treatment, fMRI scans as well as an additional blood draw at all other MRI visits. The 1st phase of the study entered the R61 no cost extension at the end of the project period & due to limited funds, participants will no longer be receiving up to 4 scans. Participants who consent at UNC on or after 11/1/18 will receive only pre- and post-treatment scans (2 scans total). **The R61 no cost extension has ended and the study has entered the larger R33 phase of the study and participants will continue to receive only pre and post treatment scans (2 total) and no bloodwork will be collected starting summer 2020 for new participants. \*\*No new enrollment to imaging at UNC will occur with the approval of the June 2022 NCE amendment.**
- 6) A post-treatment clinical characterization visit
- 7) A post-treatment 7T scan

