## 9 STATISTICAL CONSIDERATIONS

### 9.1 SAMPLE SIZE DETERMINATION

**Aims 1, 2, and 5:** To evaluate whether BATA produces changes in neural responses to reward anticipation and reward outcomes that (1) exceed our *a priori* target engagement criteria; (2) exceed changes due to a comparison treatment; and (3) does not impact neural responses to threat. To evaluate relations between BATA dose and neural target engagement by examining changes in reward responding with fMRI scans 8, 12 and 16 weeks after starting the 15-week treatment.

Power is calculated for Aim 1 fMRI analyses because of its smaller sample, and the Aims that involve all 210 participants will have higher power because of the larger sample and optimized BATA dose. For Aim 1 we will enroll 30 outpatients per group to have complete data from 25 per group. Based on our pilot data demonstrating increased right CN activation during reward anticipation and decreased rACC activation during reward outcomes, we calculated an effect size of approximately  $z=4.1$ . Conservatively, we estimate the effect size for the increased right CN activation and reduced rACC activation will be in the range of  $z = (0.75-1.25)$ . Our models will thus have  $>90\%$  power at  $\alpha=0.025$ .

**Aims 3 and 4:** To evaluate the effects of BATA versus MBCT on anhedonic symptoms, functional outcomes, and behavioral indices of reward sensitivity. Our power analysis addresses the effects of BATA versus MBCT on SHAPS scores (conducted with Gpower) as an ANCOVA with two groups and two timepoints. With 65 subjects per treatment group with complete data at post-treatment,  $\alpha = .05$ , and assumed correlation between assessments of 0.35 (based on preliminary studies), we will have 98% power to detect small ( $f = .2$ ) effects. Pilot data in depressed patients indicated a large effect from pre-to post-treatment ( $d=1.24$ ,  $f = .62$ ), and we are powered to detect these effects. We are 80% powered to detect the interactions with effects as small as  $f = .14$ .

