Exploratory Connectivity Analyses: Mesocorticolimbic connectivity in central to anhedonia. We will explore task-dependent correlations between ROIs using a psychophysiological interactions approach as in our prior work. Timeseries will be extracted from ROIs using FSL Featquery for each participant and trial type and correlation values will be transformed using a Fisher r-to z transformation. We also conduct whole-brain connectivity analysis, with a particular emphasis on the salience network (i.e., dorsal anterior cingulate cortex, anterior prefrontal cortex, and anterior insula), by segmenting the brain based on a probabilistic atlas, while correcting for multiple comparisons at the familywise error rate of  $p < .05$ .

**Secondary Analysis:** Secondary data analysis will be conducted examining relationship between psychological symptoms and patterns of brain activation in the functional neuro data. Data will be transferred from UNC to Duke to be analyzed by Duke study team members.

**Aims 1 and 5:** Only patients who complete baseline measures will receive BATA, and those who complete at least one BATA session will participate in post-treatment assessments (ITT, estimating ~90% of sample). We will compare fMRI activation in regions of interest at pre- and post-treatment. Primary analyses will address changes in regional brain activation from baseline to post-treatment.

Models will include motion parameters, gender, and age as covariates. The design is a 2 (BATA vs MBCT) X 3 (CN, rACC, amygdala) X 2 (pretreatment vs post-treatment) ANCOVA testing the change from pre- to post-treatment as moderated by treatment group and brain region in the outcome variables controlling for the covariates. Post-hoc comparisons will compare change across each region. Note that CN and rACC activation values are derived from the MID task whereas amygdala activation values are derived from the threat task.

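### The Aims 3 and 4 model compares change scores and does not adjust for each outcome's baseline value, which gives up precision the trial could have at almost no cost

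*Combined protocol and SAP*

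**What the plan says.** For Aims 3 and 4, section 9.2 sets out a repeated-measures ANCOVA with treatment condition, outcome measure, time (pre, post) and their interactions. Its purpose is to test whether change over time differs between BATA and MBCT. The covariates are stated in one sentence: "We will include gender and age as covariates in these models". On interpretation it adds: "The interaction tests will assess mean differences at each time point as well as differences in the degree of change between the groups". Nowhere is an outcome adjusted for its own baseline value, and no constraint of equal group means at pre-treatment is stated.

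The power paragraph for these aims (section 9.1) concerns SHAPS, with 65 completers per group, alpha 0.05 and an "assumed correlation between assessments of 0.35 (based on preliminary studies"). It reports 98% power at f = 0.2. For the smaller effect it says "We are 80% powered to detect the interactions with effects as small as" f = 0.14.

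The Aims 1 and 5 imaging model in section 9.2 has the same form, "testing the change from pre- to post-treatment as moderated by treatment group and brain region", with motion, gender and age as covariates.

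**The concern.** The word ANCOVA suggests baseline adjustment, but here the covariates are gender and age, and the pre-treatment score enters as an outcome. With two timepoints and complete data, the group-by-time interaction is the between-group difference in mean change. That contrast subtracts the whole baseline value, although a correlation of 0.35 supports subtracting only part of it. The rest is added noise.

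The stakes are greatest for modest effects. Change in SHAPS is listed as a primary endpoint in the synopsis, and the comparator is an active psychotherapy whose recipients are also expected to improve (section 2.3.2). The large pilot effect in section 9.1 (d = 1.24) is a pre-to-post effect and not a contrast between treatments. A modest between-group difference is therefore a realistic prospect, and at f = 0.14 the planned test misses it about one time in five.

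**Working it through.** **Inputs.** From section 9.1: 65 per group (N = 130), r = 0.35, alpha 0.05, f = 0.20 and 0.14. The SHAPS SDs are not given, so let the pre SD be 1 and the post SD be k. Equal SDs (k = 1) are implicit in the power formula below; other values of k are assumptions.

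**1. Reproduce the plan's power.** For a group-by-time interaction with two timepoints, the noncentrality is λ = 2Nf²/(1−r), with 1 and 128 degrees of freedom.
- f = 0.20: λ = 2 × 130 × 0.04 / 0.65 = 16.0, power 97.8% (stated 98%).
- f = 0.14: λ = 2 × 130 × 0.0196 / 0.65 = 7.84, power 79.4% (stated 80%).

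Other readings do not fit at f = 0.20: a between-groups main effect gives 78.7%, a plain ANCOVA 61.9%, an ANCOVA with f² divided by 1−r² 67.6%, and the interaction formula without r 89.3%. The plan was therefore powered on the change-score test, and plan and power agree. In this design a difference in change of D SDs corresponds to D = 4f, so the two effects are 0.80 and 0.56 SD.

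**2. Variance of the treatment effect (per-participant terms).**
- Change score: 1 + k² − 2rk.
- Baseline-adjusted: k²(1 − r²).
- Proportional reduction: (1 − rk)² / (1 + k² − 2rk).

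At k = 1 the change-score variance is 2 × 0.65 = 1.30 and the adjusted variance is 1 − 0.1225 = 0.8775. The reduction is 0.4225 / 1.30 = 32.5%. Put another way, 65 × 0.675 ≈ 44 per arm with adjustment match the precision of 65 per arm on change scores.

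**3. Range over the SD ratio** (r = 0.35, 65 per arm, planned power held at 79.4%):

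| Post/pre SD ratio k | Change variance | Adjusted variance | Reduction | Adjusted power |
|---|---|---|---|---|
| 0.8 | 1.080 | 0.562 | 48.0% | 97.1% |
| 1 | 1.300 | 0.8775 | 32.5% | 92% |
| 1.25 | 1.688 | 1.371 | 18.8% | 86.9% |
| 1.5 | 2.200 | 1.974 | 10.3% | 83.5% |
| 2 | 3.600 | 3.510 | 2.5% | 80.3% |

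The reduction is never negative. It reaches zero at k = 1/0.35 = 2.86.

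**4. Other figures at k = 1.** At 0.80 SD, power goes from 97.8% to 99.8%. The difference detectable with 80% power falls from 0.565 to 0.464 SD. An unadjusted comparison of post-treatment means has variance 1.00, so adjustment reduces it by r² = 12.25%; its power at 0.56 SD is 88.7%. With equal SDs and r below 0.5, the change score is thus noisier than ignoring the baseline altogether.

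**5. Simulation check** (20,000 trials per ratio, 65 per arm), change-score against adjusted power: k = 1, 79.1% and 91.8%; k = 1.25, 79.1% and 86.7%; k = 1.5, 79.2% and 83.2%; k = 2, 79.5% and 80.0%. These sit slightly below the formula because the baseline slope is estimated.

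**The case against.** Nothing here is invalid. The plan asks about differential change, its model answers that question, and its power matches its model. At f = 0.20 there is almost nothing to gain. All of that stands, and it is why this is a recommendation about efficiency and not a report of an error.

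The 32.5% also depends on equal SDs, which the entry rule makes doubtful. Section 6.3 says of R33 that "we will no longer stratify groups based on SHAPS score as all participants will have SHAPS scores 30 or greater", and truncating the baseline narrows its SD. As an illustration, suppose a normal baseline, equal SDs before truncation and r = 0.35 after selection. If the cut-off removes the lower 30%, 50% or 70%, the ratio is about 1.34, 1.51 or 1.68 and the reduction about 15%, 10% or 6%. This stands: 32.5% should be read as a figure for equal SDs and not as the central expectation.

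Completers may exceed 65 per arm. The aims cover 105 per arm, and section 5.4 cites about 81% retention between imaging sessions. If that applied to SHAPS, 105 × 0.81 ≈ 85 would complete. Planned power at 0.56 SD would then be about 89%, rising to 97% at k = 1 or 92% at k = 1.5. The power gain shrinks, but the proportional variance reduction does not depend on n.

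Three further points bear on the fix. SHAPS is scheduled more than once before treatment (section 1.3), so baseline must be defined; a change score needs the same definition. Section 4.1 presents Aim 5 as a replication of Aim 1, so changing only Aim 5 loosens that match. The document is dated October 2023, R61 data have already informed the go/no-go decision, and therapists and participants know the assignment, so a late change of primary test needs care. The documents do not say whether the final analysis has begun.

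**Conclusion.** The concern holds. The Aims 3 and 4 test is a change-score comparison without adjustment for the outcome's baseline, and the plan's own power figures confirm that reading. Under randomization, the adjusted model estimates the same treatment effect and, apart from the degree of freedom spent on the slope, is at least as precise. For SHAPS at r = 0.35 the variance reduction runs from 32.5% at equal SDs to 2.5% when the post SD is twice the pre SD, and is larger if the post SD is the smaller one. Power at f = 0.14 with 65 per arm moves from about 79% to between 80% and 92% over ratios of 2 down to 1.

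These figures apply to the single-outcome SHAPS test that section 9.1 powers, and they ignore variance explained by gender and age. The full model also has outcome measure as a factor. No correlation is given for PRT, EEfRT, functional outcomes or the imaging regions, so no size is claimed for them.

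**What to change.** - For each Aim 3 and 4 outcome, make the primary treatment test a model of the post-treatment value on treatment, with that outcome's baseline, gender and age as covariates. State which pre-treatment measurement is the baseline. Keep within-group change as description.
- Restate the power in section 9.1 for this model, with the assumed pre and post SDs.
- Prespecify how missing baselines are handled. Section 9.2 only promises to note participants who "had PRT & EffRT reward tasks data omitted during COVID-19 times". One option is a mixed model with pre and post as outcomes and equal group means at pre-treatment, which keeps participants who have only one of the two values. The plan should name one primary estimator.
- Use the same form for the Aim 5 region-of-interest analysis, with the pre-treatment value as covariate. Leave the Aim 1 go/no-go analysis unchanged. Reporting the change-score result for Aim 5 alongside would preserve the comparison with Aim 1.
- As minor additions, include phase (R61 or R33) in the pooled models, and baseline SHAPS, which largely carries the R61 stratum, in the models for other outcomes.

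The cost is SAP wording, a revised power paragraph and a few degrees of freedom; no new data are needed. Section 4.1 says "imaging of new participants will end", so participants enrolled after that point lack imaging values under either model. The change should be made before the final analysis. If between-group results on these outcomes have already been seen, report the adjusted model as a labelled supplementary analysis.
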